#### 10.7.4 Anti-AMG 145 Antibodies

The incidence and percentages of subjects who develop anti-AMG145 antibodies (binding and neutralizing) at any time will be tabulated.

## 10.7.5 Exposure to Investigational Product

Descriptive statistics will be produced to describe the patient-month exposure to investigational product, the categorical representation of dose received, and the cumulative dose used by defined groups.

Exposure definitions are provided in Section 6.3.

# 11. Changes From Protocol-specified Analyses

The protocol specifies treatment-related adverse events will be tabulated by system organ class and preferred term for each treatment arm. This tabulation will not be included in the primary analysis. Instead treatment-related adverse events will be included in the overall adverse event summary and a tabulation of events of interest will be included.

#### 13. Data not Covered by This Plan

Currently there are no pre-planned analyses for the biochemical cardiovascular biomarker objective.

Statistical Analysis Plan: 20110271

Dated: 26 May 2018 Page 22 of 27

14. Appendices

Statistical Analysis Plan: 20110271

Dated: 26 May 2018 Page 23 of 27

# Appendix A. Analytical Study Week Assignments

Selected endpoints will be summarized by scheduled study visits in descriptive analyses. Since the actual visits may not exactly coincide with their scheduled visit day, the actual visit day is mapped to the study visit generally by non-overlapping consecutive intervals covering the entire time continuum, with scheduled visit time being the center of each interval. The mapping intervals for all distinct schedules are summarized in the following table.

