7.1.2.1 Weeks 2 and 10 (± 7 Days) Non-parent Subjects Only – Mandatory for All Apheresis Subjects, Optional for Non-apheresis Subjects

- Vital signs: sitting blood pressure (BP), heart rate (HR)
- AEs/ADEs/SAEs
- Concomitant medications
- Blood draw for fasting lipids (≥ 9 hour fasting sample), ApoA1, ApoB, Lp(a), PK (AMG 145) and PCSK9
- Administer IP to subjects (as applicable for Q2W subjects)

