- i FSH = in applicable subjects for study entry only – see [exclusion criteria](#).
- j Pregnancy testing will occur every 6 months and during screening. **Additional pregnancy testing may be performed at the discretion of the investigator.**
- k eGFR at screening only.
- l Dose frequency may vary based on titration. Please refer to [section 6.1.1](#).
- m PCSK9 only.
- n For adolescent subjects (as defined in the study glossary), growth parameters (height, weight, and Tanner staging; see [Appendix E](#)) will be performed on D1, every 48 weeks, and at EOS. Documentation of historical assessments of height, weight and Tanner stage for adolescent subjects should be obtained on D1 (or as soon as possible after enrollment). If Tanner staging cannot be performed on Study Day 1, it should be performed along with height and weight at the next scheduled study visit, and then every 48 weeks starting at the week 48 visit. Adult subjects should follow the schedule for Physical Exam and Body weight as above, and will not undergo Tanner staging.

NON-PARENT / NON-APHERESIS SUBJECTS ONLY:

Study Day / Timepoint	Screening ^a	Day 1 OL ^b	Optional Visits (Weeks 2,10 ^c)	Interval Visits (Weeks 4, 6, 8, 16, 20)	Quarterly Visits ^d (Every 12 weeks)	EOS/ ET OL
General Procedures						
Informed consent	X					
Vital Signs (HR, BP)	X	X	X	X	X	X
AEs/ADEs/SAEs	X	X	X	X	X	X
Concomitant medication	X	X	X	X	X	X
Physical exam	X					X
Body weight	X					X
Growth parameters ^o		X ^o			X ^o	X ^o
12 Lead ECG	X					X
Central Laboratory						
Fasting plasma lipids, Lp(a), ApoA1, ApoB ^e	X	X	X	X ^f	X	X
PK samples (AMG 145), PCSK9	X ^g	X	X	X ^f	X	X
Chemistry	X	X			X	X
Hematology	X	X			X	X
HbA1c	X	X			X	X
Coagulation	X	X			X	X
hsCRP		X			X	X
Fasting Vitamin E		X ^h			X ^h	X
Biomarkers (blood)		X			X ⁱ	
Anti-AMG 145 antibodies		X			X ^j	X
Serum pregnancy (females of childbearing potential) and FSH	X ^{k,l}	X ^k			X ^l	X
Urinalysis, eGFR	X ^m	X				X
Investigational Product						
IP administration, QM or Q2W ⁿ		X		X	X	

Footnotes defined on the next page.

- a Screening is for all non-parent study subjects.
- b D1 = day of first administration of investigational product for the open-label.
- c Week 2 and week 10 assessments and visits are not compulsory. They may be performed according to the subject's availability.

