#### Handling multiple records assigned to an analytical study week:

If there is more than one record in a study week interval, the analytical record for that specific study week will be defined as followings:

The record closest to the scheduled study day of the specific study week (7\*study week+1) will be selected. If two records are equidistant from the scheduled day, then the earlier record will be chosen. If there are multiple records on the same day, the last record will be used.

Handling multiple records assigned to an analytical study week for apheresis patients:

For apheresis patients, their apheresis date is aligned with the scheduled visit. As such, when multiple records available during a visit window, the one on the same day as apheresis should be selected. If no apheresis record can be found during the visit window, then the records will be mapped using the target visit date instead. If both pre-and post-apheresis assessments were performed, the pre-apheresis assessment will be used for summary for the sake of this SAP.

Statistical Analysis Plan: 20110271

Dated: 26 May 2018 Page 24 of 27

Table A.1 Visit Windows for Labs, hsCRP, Antibodies and Vitamin E

		Chemistry,			
		Coagulation,			
	Scheduled	Hematology,			
Scheduled	Visit Study	hsCRP,	Anti-AMG 145	Direct LDL,	Fasting Vitamin
Visit Week	Day	HbA1c	antibodies	Direct VLDL	E
Week 4	29			2-42	
Week 6	43				
Week 8	57			43-70	
Week 12	85	2-126	2-126	71-98	2-126
Week 16	113			99-126	
Week 20	141			127-154	
Week 24	169	127-210	127-210	155-210	127-210
Week 36	253	211-294	211-294	211-294	211-294
Week 48 / Year 1	337	295-378	295-504	>=295	295-420
Week 60	421	379-462			
Week 72	505	463-546			421-588
Week 84	589	547-630			
Week 96 / Year 2	673	631-714	505-882		>=589
Week n	n*7+1	From (n-6)*7+1 to (n+6)*7			
Week 156 / Year 3	1093		883-1260		
Week 204 / Year 4	1429		1261-1638		
Week 264 / Year 5	1849	an ingramantal h	>=1639		

Where n = 108, 120, 132 and so on, incremental by 12, until 264

Statistical Analysis Plan: 20110271

Dated: 26 May 2018 Page 25 of 27

Table A.2 Visit Window for Vital Signs, Lipid Labsa, Lp(a) PK and PCSK9

		Vital Signs, Fasting plasma lipids a , ApoA1, ApoB, Lp(a), PK, PCSK9		
Scheduled Visit Week	Scheduled Visit Study Day	Parent Study Rollover	Non-Parent / Non-Apheresis	Non-Parent / Apheresis
Week 2	15			2-21
Week 4	29	2-35	2-35	22-35
Week 6	43	36-49	36-49	36-49
Week 8	57	50-70	50-70	50-60
Week 9	64			61-67
Week 10	71			68-77
Week 12	85	71-98	71-98	78-98

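### SAP Table A.2 has no week 2 or week 10 row for non-parent, non-apheresis subjects, so their optional draws at those visits are usually dropped and sometimes reported as week 4, 8 or 12

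*SAP*

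**What the plan says.** **Protocol.** Section 7.1.2.1 provides week 2 and week 10 visits (±7 days) for non-parent subjects: "Mandatory for All Apheresis Subjects, Optional for Non-apheresis Subjects". Vital signs are taken, and blood is drawn for fasting lipids, ApoA1, ApoB, Lp(a), AMG 145 and PCSK9. The non-parent / non-apheresis schedule in Appendix A gives these visits their own optional column, with the footnote "Week 2 and week 10 assessments and visits are not compulsory". The notes to the study schema say that parent-study subjects should not have them.

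**SAP.** Appendix A introduces its windows with "The mapping intervals for all distinct schedules are summarized in the following table". Table A.2 covers vital signs, the lipid panel (without direct LDL and direct VLDL), ApoA1, ApoB, Lp(a), PK and PCSK9. Its three window columns are, in order, parent rollover, non-parent / non-apheresis and non-parent / apheresis. The relevant rows are:

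- "Week 4 29 2-35 2-35 22-35"
- "Week 8 57 50-70 50-70 50-60"
- "Week 10 71 68-77" (the single window belongs to the apheresis column)
- "Week 12 85 71-98 71-98 78-98"

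The week 2 row is likewise filled only for apheresis subjects (days 2-21). When several records share a window, "The record closest to the scheduled study day of the specific study week (7\*study week+1) will be selected"; a tie goes to the earlier record. SAP 10.6.1 promises secondary-endpoint summaries at all scheduled visits and time points.

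**The concern.** Weeks 2 and 10 are the visits that distinguish the non-parent / non-apheresis schedule from the rollover schedule, yet the two columns of Table A.2 are identical. No SAP rule says what happens to an optional draw. It is therefore treated as a candidate for whichever neighbouring week's window contains it.

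Under Protocol 6.1.1, non-apheresis subjects start on QM dosing, and dose changes are foreseen at week 12 or 24. Weeks 2 and 10 then lie about 14 days after a dose, while weeks 4, 8 and 12 lie at the end of a dosing interval. The protocol's first-in-human summary (Section 2.2.1) shows why that difference matters. The LDL-C nadir came within 2 weeks of dosing. After 420 mg, mean PCSK9 stayed below 15 ng/mL until day 11 and then moved back to or toward a baseline of about 200 to 280 ng/mL. A mid-interval value in an end-of-interval row would tend to make the LDL-C percent change, the 15% responder rate and the PCSK9 change look better than they were at that visit.

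**Working it through.** **Inputs.** Target day = 7 × week + 1 (SAP Appendix A). Visit tolerance is ±7 days (Protocol 7.1.2.1, 7.1.2.2 and 7.1.2.5). Windows are those of Table A.2, non-parent / non-apheresis column: week 4 = 2-35, week 6 = 36-49, week 8 = 50-70, week 12 = 71-98.

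**Reproducing the table.** Start the first window on day 2 and end each window on the day before the midpoint between adjacent targets, rounding a half-day midpoint up.

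- With weeks 4, 6, 8, 12, 16, 20 and 24 (36 following), this gives 2-35, 36-49, 50-70, 71-98, 99-126, 127-154 and 155-210, which is the non-parent / non-apheresis column.
- With weeks 2, 9 and 10 added, it gives the apheresis column.

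The non-apheresis column is thus what the table's own convention yields when weeks 2 and 10 are left out.

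**Where allowed optional draws fall.**

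| Nominal visit | Target day | Allowed days | Window that contains them |
|---|---|---|---|
| Week 2 | 15 | 8-22 | Week 4: all 15 days |
| Week 10 | 71 | 64-78 | Week 8: days 64-70 (7 days); week 12: days 71-78 (8 days) |

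**Applying the closest-record rule when the neighbouring visits also occur within ±7 days, in order.**

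- *Week 2 with week 4.* There are 15 × 15 = 225 day pairs. Removing the one pair on the same day (22, 22) leaves 224. The week 2 draw is dropped in 209. In the other 15, week 4 takes place on day 36 = 29 + 7, which Table A.2 maps to week 6. The week 2 draw is then alone in the week 4 window and is reported as week 4.
- *Week 10 with weeks 8 and 12.* There are 15 × 15 × 15 = 3375 day triples. Removing 15 with week 8 and week 10 both on day 64, and 15 with week 10 and week 12 both on day 78, leaves 3345. The week 10 draw is dropped in 3330. In the other 15, week 10 is on day 78 and week 12 on day 92. Both are 7 days from day 85 (85 − 78 = 92 − 85 = 7), so the earlier one, the week 10 draw, is reported as week 12.

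These are counts of day combinations, not probabilities.

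**When a neighbouring visit is missed.** With no week 4 visit, the week 2 draw is reported as week 4. With no week 8 visit, a week 10 draw on days 64-70 is reported as week 8. With no week 12 visit, a week 10 draw on days 71-78 is reported as week 12.

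**The case against.** The strongest reply is that the omission is a choice. The visits are optional, the schedule keeps them apart from the interval visits, and only weeks 4, 6, 8, 16 and 20 carry mandatory interval labs. Table A.2 gives windows to exactly those and the quarterly visits. It has one column per schedule, Appendix A speaks of selected endpoints, and SAP 10.6.1 notes that visits vary with apheresis status. This may well be the intent, but it does not settle the matter. The SAP never says that optional draws are excluded, and the selection rule as written still admits them.

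Three stronger readings are tempting, and the documents do not support them.

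- *Optional draws are always misassigned.* Lying inside a window is not the same as being reported for that week. With compliant neighbouring visits the draw is nearly always discarded. Relabelling needs a missed or out-of-window neighbour, week 4 on day 36, or the day 78 / day 92 tie.
- *The data are never reported.* SAP 10.6.3 plans AMG 145 and PCSK9 concentration-time profiles by nominal time, which need not use Table A.2. The loss is clear only for the by-visit lipid, apolipoprotein, Lp(a) and vital-sign summaries. Week 6, also mid-interval under QM dosing, does have its own window.
- *The size of the distortion can be read from the first-in-human data.* Those are single doses in healthy subjects. They support a direction, not a magnitude in repeatedly dosed severe FH.

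**Conclusion.** Wrong as written, with small impact. Followed literally, the rule can report a week 2 draw as week 4, or a week 10 draw as week 8 or week 12. More often it removes such draws from the by-visit summaries without saying so. The direction, overstated LDL-C and PCSK9 reduction in end-of-interval rows, assumes QM dosing through week 12 and a time course broadly like the one seen after single doses. The number of affected records cannot be given, because the documents state neither attendance at the optional visits nor the rate of missed neighbouring visits. All analyses are descriptive, so no error rate or power is involved. The primary endpoint, incidence of treatment-emergent adverse events, does not use these windows.

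**What to change.** Keep the existing Table A.2 windows for the non-parent / non-apheresis cohort and add two statements to SAP Appendix A:

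1. A record collected at a nominal week 2 or week 10 visit is not eligible to be the analysis record for week 4, 8 or 12.
2. Such records are summarised by nominal visit in their own week 2 and week 10 rows, with N shown.

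This is a text edit and needs no new data. The cost is two sparse rows and a few more missing week 4, 8 and 12 values. One example is a subject whose week 4 visit fell on day 36, which would still map to week 6.

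New midpoint windows (week 8 = 50-63, week 10 = 64-77, week 12 = 78-98) look like the natural alternative but are worse here. They would send a compliant week 8 visit on day 64 to week 10. In subjects who skipped the optional visit, they would also label late week 8 records (days 64-70) and early week 12 records (days 71-77) as week 10.

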#### Handling multiple records assigned to an analytical study week:

If there is more than one record in a study week interval, the analytical record for that specific study week will be defined as followings:

The record closest to the scheduled study day of the specific study week (7\*study week+1) will be selected. If two records are equidistant from the scheduled day, then the earlier record will be chosen. If there are multiple records on the same day, the last record will be used.

Handling multiple records assigned to an analytical study week for apheresis patients:

For apheresis patients, their apheresis date is aligned with the scheduled visit. As such, when multiple records available during a visit window, the one on the same day as apheresis should be selected. If no apheresis record can be found during the visit window, then the records will be mapped using the target visit date instead. If both pre-and post-apheresis assessments were performed, the pre-apheresis assessment will be used for summary for the sake of this SAP.

Statistical Analysis Plan: 20110271

Dated: 26 May 2018 Page 24 of 27

Table A.1 Visit Windows for Labs, hsCRP, Antibodies and Vitamin E

		Chemistry,			
		Coagulation,			
	Scheduled	Hematology,			
Scheduled	Visit Study	hsCRP,	Anti-AMG 145	Direct LDL,	Fasting Vitamin
Visit Week	Day	HbA1c	antibodies	Direct VLDL	E
Week 4	29			2-42	
Week 6	43				
Week 8	57			43-70	
Week 12	85	2-126	2-126	71-98	2-126
Week 16	113			99-126	
Week 20	141			127-154	
Week 24	169	127-210	127-210	155-210	127-210
Week 36	253	211-294	211-294	211-294	211-294
Week 48 / Year 1	337	295-378	295-504	>=295	295-420
Week 60	421	379-462			
Week 72	505	463-546			421-588
Week 84	589	547-630			
Week 96 / Year 2	673	631-714	505-882		>=589
Week n	n*7+1	From (n-6)*7+1 to (n+6)*7			
Week 156 / Year 3	1093		883-1260		
Week 204 / Year 4	1429		1261-1638		
Week 264 / Year 5	1849	an ingramantal h	>=1639		

Where n = 108, 120, 132 and so on, incremental by 12, until 264

Statistical Analysis Plan: 20110271

Dated: 26 May 2018 Page 25 of 27

Table A.2 Visit Window for Vital Signs, Lipid Labsa, Lp(a) PK and PCSK9

		Vital Signs, Fasting plasma lipids a , ApoA1, ApoB, Lp(a), PK, PCSK9		
Scheduled Visit Week	Scheduled Visit Study Day	Parent Study Rollover	Non-Parent / Non-Apheresis	Non-Parent / Apheresis
Week 2	15			2-21
Week 4	29	2-35	2-35	22-35
Week 6	43	36-49	36-49	36-49
Week 8	57	50-70	50-70	50-60
Week 9	64			61-67
Week 10	71			68-77
Week 12	85	71-98	71-98	78-98
Week 16	113	99-126	99-126	99-126
Week 20	141	127-154	127-154	127-154
Week 24	169	155-210	155-210	155-210
Week n	n*7+1	From (n-6)*7+1 to (n+6)*7	From (n-6)*7+1 to (n+6)*7	From (n-6)*7+1 to (n+6)*7

Where n=36, 48, 60 and so on, incremental by 12, until 264. a Lipid panel excluding Direct VLDL and Direct LDL.

Table A.3 Visit Window for Endpoints Collected only at the End of Study

Scheduled Visit Week	Weight, Physical Exam, Urinalysis, 12 Lead ECG,eGFR
EOS	>1

Statistical Analysis Plan: 20110271

Dated: 26 May 2018 Page 26 of 27

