2.2.4.4 Aggregate Safety Data From Completed Phase 2 Studies

Adverse event data from completed clinical studies suggest that AMG 145 has an acceptable safety profile up to the highest dose tested (420 mg). Specifically:

- In completed phase 2 studies, subjects treated with AMG 145 (n = 961) experienced a higher overall incidence of treatment emergent adverse events compared with placebo (n = 301) (57% and 48%, respectively); however, there was no relationship between the dose or dosing frequency of AMG 145 and the incidence of treatment emergent adverse events.
- In completed phase 2 studies, adverse events with a subject incidence of at least 2% in the AMG 145 group and exceeding the placebo incidence by at least 1% were as follows (AMG 145, placebo): nasopharyngitis (8.2%, 6.6%), myalgia (2.7%, 1.0%), and nausea (2.7%, 1.7%).
- In completed phase 2 studies, the overall incidence of serious adverse events was similar between the AMG 145 and placebo groups (2.1% and 1.3%, respectively). No individual serious adverse event was reported in more than 2 (0.2%) subjects treated with AMG 145 in these studies.

There was a higher incidence of creatine kinase (CK) elevations in the AMG 145 group compared with placebo. These elevations were generally associated with obvious precipitating events in the form of strenuous physical activity. All of these events were transient (one laboratory abnormality followed by normal laboratory values), resolved spontaneously, and did not lead to discontinuation of investigational product (IP).

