6.1.3.1 Elevation of Creatine Kinase (CK)

If CK is > 5x ULN, CK must be retested before IP is administered. In addition, investigators will ask study subjects to promptly report muscle pain, cramps, or weakness especially if accompanied by malaise or fever. If such symptoms occur and no scheduled study laboratory assessments are performed, the subject's CK levels should be measured by unscheduled assessment. If CK is > 5x ULN, the subject must be instructed as soon as possible to discontinue statin, other applicable lipid background therapy, and IP and CK must be retested before statin, other lipid background therapy, and/or IP (AMG 145) administration can be continued. A sample for urinalysis must be collected and sent to the central laboratory if CK is elevated > 10x ULN on retest as per table below.

The following rules apply for scheduled laboratory assessments and for unscheduled CK measurements:

CK at scheduled or unscheduled visit	CK on retest	Investigational Product and/or Statin Administration
> 5x ULN	> 10x ULN	Discontinue both statin and IP ^a . Collect urine sample for urinalysis. Contact Amgen Medical Monitor.
	> 5x to ≤ 10x ULN	Discontinue statin and retest CK before administration. Consider continuing IP if alternative explanation.
	≤ 5x ULN	Consider continuing statin and IP

^a CK elevations > 10x ULN that have been confirmed to be secondary to myocardial infarction do not require discontinuation of IP

If muscular symptoms are severe and cause daily discomfort, even if the CK levels are elevated to ≤ 5x ULN, reduction of statin dose, discontinuation of statin, or introduction of an alternative statin may be considered at the lowest dose and with close monitoring.

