Appendix B. Additional Safety Assessment Information

Adverse Event Toxicity Grading Scale

Refer to the NCI Common Terminology Criteria for AEs (CTCAE) Version 4.0 for AE grading and information. The CTCAE is available at the following link:

http://ctep.cancer.gov/protocolDevelopment/electronic_applications/ctc.htm.

When an AE cannot be graded by CTCAE v4.0 the following severity grade may be used:

Grade	Amgen Standard Adverse Event Severity Scoring System
1	MILD: Aware of sign or symptom, but easily tolerated
2	MODERATE: Discomfort enough to cause interference with usual activity
3	SEVERE: Incapacitating with inability to work or do usual activity
4	LIFE-THREATENING: Refers to an event in which the patient was, in the view of the investigator, at risk of death at the time of the event. (This category is not to be used for an event that hypothetically might have caused death if it were more severe.)
5	FATAL

Drug-induced Liver Injury Reporting & Additional Assessments

Reporting

To facilitate appropriate monitoring for signals of DILI, cases of concurrent AST/ALT and TBL elevation according to the criteria specified in [Section 6.1.3.2](#) (3x ULN for AST/ALT, 2x ULN for TBL, and **ALP < 2x ULN**) require the following:

- The event should be reported to Amgen as a serious adverse event within 24 hours of discovery or notification of the event (ie, before additional etiologic investigations have been concluded)
- The appropriate eCRF (eg, adverse event eCRF) that captures information necessary to facilitate the evaluation of treatment-emergent liver abnormalities should be completed.

Other events of hepatotoxicity and potential DILI should be reported as serious adverse events if they meet the criteria for a serious adverse event defined in [Section 9.2.1](#).

Additional Clinical Assessments and Observation

All subjects in whom IP and/or background lipid therapy is withheld due to potential DILI or who experience AST/ALT elevations $>3x$ ULN should undergo a period of “close observation” until abnormalities return to normal or to the subject’s baseline levels.

Assessments that should be performed during this period include:

- Repeat liver chemistries within 24-48 hours (ALT, AST, ALP, TBL); in cases of TBL $\geq 2x$ ULN, **ALP $< 2x$ ULN**, or AST/ALT much greater than $3x$ ULN, retesting should be performed within 24 hours

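### SAP Appendix A gives the scheduled-visit record no priority, so a retest can replace the abnormal value that prompted it in the by-visit laboratory tables; the material gap is creatine kinase

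*SAP*

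**What the plan says.** SAP Appendix A maps actual visit days to study weeks by "non-overlapping consecutive intervals covering the entire time continuum". Table A.1 makes the chemistry windows 84 days wide from week 24 on, and the week 12 window runs from day 2 to day 126. When several records fall in a window, the one kept is "The record closest to the scheduled study day of the specific study week". Two further rules apply: "If two records are equidistant from the scheduled day, then the earlier record will be chosen", and "If there are multiple records on the same day, the last record will be used". Apheresis subjects have a different first rule: "when multiple records available during a visit window, the one on the same day as apheresis should be selected". The target day is their fallback when no apheresis-day record exists. Nothing in Appendix A separates scheduled from unscheduled records.

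The protocol creates unscheduled records after abnormal results. Section 6.1.3.1 states "If CK is > 5x ULN, CK must be retested before IP is administered". Appendix B asks for "Repeat liver chemistries within 24-48 hours (ALT, AST, ALP, TBL") when AST or ALT exceeds 3x ULN or treatment is withheld for possible liver injury, followed by testing at least twice weekly. Section 6.1.3 places required repeat tests at an additional visit, and section 7.1.3.4 sends all on-study samples to the central laboratory.

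On reporting, SAP 10.7.1 summarises each analyte by scheduled visit, and SAP 10.1 includes the maximum among the statistics. Protocol 10.4.2.3 bases shift tables on the worst shift from baseline to end of study. The SAP 10.7.1 shift list includes total bilirubin, ALP, AST, ALT and INR, but not CK.

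**The concern.** An abnormal result triggers the retest, and the retest then competes with that result for the single place in the window. Which value is tabulated therefore depends partly on the outcome. If the retest is lower, as it will often be, the by-visit table shows the lower value.

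This matters most for CK. Protocol 2.2.4.4 reports more CK elevations on AMG 145 than on placebo in the completed phase 2 studies, and says of them: "All of these events were transient (one laboratory abnormality followed by normal laboratory values"). That is the pattern a nearest-record rule can drop. CK has neither a shift table nor a count above a threshold, so the by-visit statistics are its only planned laboratory display, and their maximum is the figure that would reveal a single spike. Adverse event data are an incomplete backstop, because protocol 9.1.2 in general keeps laboratory abnormalities judged not clinically significant out of the event record. Safety is the primary objective of this single-arm study.

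**Working it through.** **Inputs.** The target day is 7 × week + 1 and the chemistry window is (n−6)×7+1 to (n+6)×7 (SAP Appendix A). Quarterly visits have a ±7-day window (protocol 7.1.2.5). Liver repeats come at 24–48 hours (protocol Appendix B). The CK retest is due before the next dose, with no number of days given (protocol 6.1.3.1). The distribution of visit timing is not documented and is assumed.

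**1. The plan's own figures.** Week 24 gives target day 7×24+1 = 169 and window 18×7+1 = 127 to 30×7 = 210, as printed. Target days for weeks 12 to 96 and windows for weeks 24 to 96 all reproduce. Week 12 starts at day 2 because it is the first window; the formula alone would give 43. With no gaps between windows, a retest always falls in some window, usually the same one.

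**2. When a retest wins.** Let the scheduled visit fall u days from target and the retest d days later. The retest is kept only if |u+d| < |u|, that is, u < 0 and d < 2|u|. A tie keeps the earlier record. With |u| at most 7, d must be under 14. A visit on or after the target day is never displaced by a later-day retest. A repeat on the same day always displaces the first record.

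**3. Probability given one abnormal scheduled value and one retest.** With u uniform on (−7, 7), P = (7 − d/2)/14:

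| Lag d (days) | Uniform timing | Whole-day count, of 15 offsets |
|---|---|---|
| 2 | 6/14 = 43% | 6 |
| 4 | 5/14 = 36% | 5 |
| 7 | 3.5/14 = 25% | 4 |
| 10 | 2/14 = 14% | 2 |
| 14 or more | 0% | 0 |

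If visits cluster round the target (normal, SD 3 days, truncated at ±7), the figures at 2, 4 and 7 days are 37%, 25% and 11%.

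**4. Liver monitoring.** A first repeat at 1 or 2 days, then about twice weekly for 4 weeks, displaces the scheduled value at 7 or 6 of 15 offsets. This counts any replacement, including by a retest that is still abnormal.

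**5. Unscheduled values between visits.** Take a scheduled record at −7 to +7 days and an unscheduled one on any other day of an 84-day window, all combinations weighted equally. The unscheduled value is dropped in 1140 of 1245 combinations (92%) and kept in 105 (8%). A symptom-prompted CK therefore can replace a normal scheduled value, but seldom does under this weighting.

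**6. End of study.** The ±7-day result does not cover the last visit. Week 260 is day 260×7+1 = 1821. The chemistry window containing it belongs to week 264 (days 1807–1890, target 1849), so an on-time visit is 28 days early and any retest 1 to 55 days later is closer. Liver close observation could produce such a retest; the CK rule, tied to the next dose, may not.

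**The case against.** The nearest-record rule is prespecified and reproducible, the study is descriptive, and these are secondary safety displays. The specific objections are these.

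- **The premise is an inference from silence.** Appendix A never says that unscheduled records compete, and SAP 10.7.1 speaks of scheduled visits. This stands. But windows covering all days, with no exclusion, lead a programmer who follows the text to let a retest win.
- **Liver values.** A reader might infer that abnormal liver results are hidden. The documents do not support that. Protocol 10.4.2.3 uses the worst shift, the SAP list covers AST, ALT, ALP and bilirubin, SAP section 11 does not withdraw the rule, and combined elevations meeting the liver-injury criteria are reported as serious adverse events. What remains is that SAP 10.7.1 neither repeats the worst-value basis nor says whether unscheduled values count.
- **Direction.** A reader might infer that replacement always favours normal values. It does not. Protocol 6.1.3.1 also orders unscheduled CK for muscle symptoms, and its table allows for a retest above 10x ULN.
- **Adverse events as a backstop.** Protocol 9.1.2 makes laboratory changes that require treatment or a change of therapy adverse events, so CK that stays high on retest should reach those tables. A strict reader could count even a temporary stop pending the retest. Whether CK that settles on retest is recorded still depends on the investigator's judgement, and an event entry does not restore the value to a laboratory table.
- **Size.** The probabilities are conditional on an abnormal value. The documents give neither its frequency nor the CK lag. Same-day replacement is implausible as a response to a central-laboratory result, and reporting delay also makes the shortest lags less likely. At a lag of 14 days or more the quarterly-visit figure is zero.
- **Apheresis subjects.** The figures do not apply where the apheresis-day rule selects the record.

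**Conclusion.** The concern holds in a limited form. As written, the selection rule lets a retest displace the abnormal scheduled value that prompted it, in subjects and windows not governed by the apheresis-day rule. At quarterly visits, and for a retest on a later day, this needs an early visit and a lag below twice the number of days early. The chance runs from 43% at 2 days to 14% at 10 days and zero from 14 days under uniform timing, and is lower if visits cluster on the target day. Visit timing and CK lag are assumptions. The figures are not the share of all CK elevations lost, and no effect on a mean or median can be derived from the documents.

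The net direction is likely, but not strictly, toward normal. The liver analytes are largely protected. CK is the material gap: a transient rise could leave the by-visit maximum, with no other planned laboratory table to show it and no certainty of an adverse event record. The plan should be changed, but this does not threaten the primary endpoint, whose tables do not use Appendix A.

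**What to change.** In SAP Appendix A, state that within each window the scheduled-visit record is selected first, and that an unscheduled or retest record is used only when the window holds no scheduled record. Leave the apheresis-day rule as it is. This reduces displacement by a later-day retest to 0 of 15 visit offsets at every lag.

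That step alone would keep unscheduled peaks out of the by-visit tables whenever a scheduled record exists, so it needs a companion. In SAP 10.7.1, add CK to the CTCAE shift-table list, and state that all shift tables use the worst post-baseline value, including unscheduled records.

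The cost is two or three sentences and minor programming, with no new data collection, provided the visit label in the database distinguishes scheduled from unscheduled records.
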